### 7.3.4. Proteinuria by Quantitative Assessment

The baseline, postbaseline, changes from baseline, and percentage change from baseline in urine protein to creatinine ratio (UPCR) and urine albumin to creatinine ratio (UACR) will be summarized overall and by Parts 1 and 2 for each visit using descriptive statistics.

The number and percentage of subjects with UPCR  $\leq$  200 mg/g versus  $>$  200 mg/g will be summarized by baseline category at Weeks 12, 24, and 48, and based on the last on-treatment value (up to 1 day after the last dose date of study drug {[KDIGO Guideline Development Staff 2013](#)}).

The number and percentage of subjects with UACR  $<$  30 mg/g versus  $\geq$  30 mg/g will be summarized by baseline category at Weeks 12, 24, and 48, and the last on-treatment value (after first dose date up to 1 day after the last dose date of study drug {[KDIGO Guideline Development Staff 2013](#)}).

Median (Q1, Q3) percentage change from baseline in UPCR and UACR over time will be plotted.

## 7.4. Vital Signs

Descriptive statistics (n, mean, SD, median, Q1, Q3, minimum, and maximum) will be provided overall and by Parts 1 and 2 for each visit and vital sign as follows:

- Baseline values
- Values at each postbaseline analysis window
- Change from baseline to each postbaseline analysis window

In the case of multiple values in an analysis window, data will be selected for analysis as described in Section [3.7.3](#).

A listing of weight, BMI, height, and vital signs will be provided.

## **7.5. Prior and Concomitant Medications**

### **7.5.1. Nonstudy-Drug Antiretroviral Medications**

Nonstudy drug ARV medications used prior to, during, or after the study (if collected), will be coded using the Gilead-modified World Health Organisation (WHO) Drug Dictionary. The WHO preferred name and drug code will be attached to the clinical database. All nonstudy-drug ARV medications will be listed. No inferential statistics will be provided.

Nonstudy-drug ARV medication with an end date one day before the first dose date of study drug will be considered as nonstudy-drug ARV medication received immediately prior to the first dose date of study drug (or pre-switch ARV used).

Nonstudy-drug ARV medication received immediately prior to the first dose date of study drug will be summarized by ARV drug class and generic name for subjects in the Safety Analysis Set. Multiple drug use (by drug class or generic name) will be counted only once per subject. Drug classes were presented alphabetically and generic names within each drug class were presented by descending order of the total frequency. No inferential statistics will be provided.

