3.2. Study Treatments

Subjects who provide written consent and meet all eligibility criteria will switch from their current regimen consisting of FTC/TDF or ABC/3TC plus a third antiretroviral agent to E/C/F/TAF FDC on Day 1.

Allowed third agents include LPV/r, ATV+RTV, ATV+COBI, DRV+RTV, DRV+COBI, FPV + RTV, SQV + RTV, ATV(no booster) EFV, RPV, NVP, ETR, RAL or DTG. See Table 4-1.

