5. INVESTIGATIONAL MEDICINAL PRODUCTS

5.1. Enrollment

This is an open-label, single arm study. All subjects will receive open-label E/C/F/TAF.

Subjects will be assigned a screening number at the time of consent. Investigators must consult with the Medical Monitor and receive written approval prior to re-screening subjects.

Prior to enrollment to Day 1, the historical genotype report and proviral DNA resistance test result must be reviewed and approved by Gilead and subject eligibility confirmed.

Once eligibility has been confirmed by Gilead, each subject will be assigned a unique subject number using an Interactive Web Response System (IWRS). Once a subject number has been assigned, it will not be reassigned to any other subject. The subject number assignment may be performed up to 3 days prior to the in-clinic Day 1 visit provided that all screening procedures have been completed and subject eligibility has been confirmed.

Eligibility and all Day 1 visit tests and procedures must be completed prior to the administration of the first dose of study drug.

The IWRS will assign open-label study drug bottle numbers at each study visit. Study drug will be dispensed to the subjects in an open-label fashion. Initiation of treatment with the study drug must take place within 24 hours after the Day 1 visit.

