##### **3.1.2. Full Analysis Set**

The Full Analysis Set (FAS) will include all the subjects who were enrolled and received at least one dose of study drug. For the FAS, all efficacy data will be included, unless specified otherwise. The FAS is the primary analysis set for the efficacy analyses.

Subjects meeting the following criteria will be excluded from the FAS:

- Subjects who took Stribild or Descovy as part of the baseline antiretroviral (ARV) regimen and thus violated the inclusion criterion.

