### 3.7. Analysis Visit Windows

#### 3.7.1. Definition of Study Day

**Study Day 1** is defined as the day when the first dose of study drug (ie, E/C/F/TAF) was taken, as recorded on the Study Drug Administration eCRF form.

**Study Days** are calculated relative to Study Day 1. For events that occurred on or after Study Day 1 date, study days are calculated as (visit date minus date of the first dose plus 1). For events that occurred prior to Study Day 1, study days are calculated as (visit date minus date of the first dose).

**Last Dose Date** is the latest nonmissing end date of study drug (E/C/F/TAF) recorded on the Study Drug Administration eCRF form with “Study Drug Permanently Withdrawn” box checked for subjects who prematurely discontinued study drug or who completed study drug according to Study Drug Completion eCRF.

If the date of last dose is missing (eg, only year of last dose is known or completely missing due to lost to follow-up) for subjects who prematurely discontinued study drug, or for subjects who completed study drug, the latest of nonmissing study drug start dates and end dates, the clinic visit dates, and the laboratory visit dates excluding the date of 30-day follow-up visit will be used to impute the last dose date. For other partial missing last dose date, please see SAP [Appendix 5](#) for details.

**Last Study Date** is the latest of nonmissing study drug start dates and end dates, the clinic visit dates, and the laboratory visit dates including the 30-day follow-up visit date for subjects who prematurely discontinued study or who completed study according to Study Completion eCRF.

**Baseline Value** for HIV-1 RNA, CD4+ cell count, CD4%, hematology, chemistry, urinalysis and urine chemistry laboratory tests, fasting glucose and lipid panels, eGFRCG, cystatin C testing, vital signs and weight, safety electrocardiogram (ECG), Visual Analogue Scale (VAS) Adherence Questionnaire, Medical Outcome Study Short Form-36 Questionnaire (SF-36), HIV Treatment Satisfaction Questionnaire (HIVTSQ) (Status at Day 1 only), Functional Assessment of Chronic Illness Therapy – Fatigue (FACIT-F), and EQ-5D is defined as the last nonmissing value obtained on or prior to Study Day 1.

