	UP ≥ 4.0	Start with 65	$1.028 \times UP - 3.70$ ; if $1.028 \times UP - 3.70 \geq 4.0$ '< 4.0'; if $1.028 \times UP - 3.70 < 4.0$
		Start with 62 or 63	$0.981 \times UP - 1.44$ ; if $0.981 \times UP - 1.44 \geq 4.0$ '< 4.0'; if $0.981 \times UP - 1.44 < 4.0$
		Start with 64 or 66	$0.980 \times UP - 1.62$ ; if $0.980 \times UP - 1.62 \geq 4.0$ '< 4.0'; if $0.980 \times UP - 1.62 < 4.0$

- c) The corrected UP results will be used for the following analysis and referred as “UP” in following text. If AVALC of the corrected UP is “< 4.0”, the AVAL of the corrected UP will be imputed as 3.9 mg/dL.

29) Unit conversion for some renal biomarkers derived from related tests with conventional units

- Urine RPB ( $\mu\text{g/L}$ ) to creatinine (mg/dL) ratio:  $1 (\mu\text{g/L}) / (\text{mg/dL}) \quad 100 \times \mu\text{g/g}$
- Urine Beta-2-microglobulin (mg/L) to creatinine (mg/dL) ratio:  $1 (\text{mg/L}) / (\text{mg/dL}) \quad 10^5 \mu\text{g/g}$
- Urine Protein (mg/dL) to creatinine (mg/dL) ratio:  $1 (\text{mg/dL}) / (\text{mg/dL}) \quad 1000 \times \text{mg/g}$
- Urine Albumin (mg/dL) to creatinine (mg/dL) ratio:  $1 (\text{mg/dL}) / (\text{mg/dL}) \quad 1000 \times \text{mg/g}$

30) Calculation of ratios

To calculate laboratory ratios (eg, urine RPB to creatinine ratio), lab value of each test in the ratio needs to be from the same accession number; if any test value used for the ratio calculation from the same accession number is missing, the ratio is not calculable (ie, missing). For urine creatinine, a value of “< 1” is handled as a missing value in the calculation of related ratios. For urine protein, a value of “< 4.0” is handled as a missing value in the calculation of UPCR.

31) Combined category of UP and UPCR

- a) First merge UP and UPCR based on the subject identifier and accession number.
- b) At each visit, based on UP to select which pair of records should be used for the analysis. That is, once a UP record is selected for that visit, the UPCR with the same accession number (if calculated) will be selected. Please note, UPCR is missing when UP < 4.0 mg/dL.
- c) Subject will be classified as “UPCR  $\leq$  200 mg/g” if UP < 4.0 mg/dL or UPCR  $\leq$  200 mg/g; Subject will be classified as “UPCR > 200 mg/g” if UPCR > 200 mg/g; Otherwise, subject will be classified as “Missing”.

32) Prior ARV

Non-study drug ARVs collected in prior ARV form with start date and stop date completely missing are considered “not concomitant”.

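### SAP 7.5.1 recognises the pre-switch regimen by one exact end date, so its table of entry regimens can omit antiretrovirals stopped on other dates that the protocol allows

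*SAP*

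**What the plan says.** SAP 7.5.1 gives one working definition of the pre-switch ARV: "Nonstudy-drug ARV medication with an end date one day before the first dose date of study drug will be considered" to be the one received immediately before study drug. A table is built on that classification: "Nonstudy-drug ARV medication received immediately prior to the first dose date of study drug will be summarized by ARV drug class and generic name", for the Safety Analysis Set. The same section also provides a listing without any date restriction: "All nonstudy-drug ARV medications will be listed".

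The date against which the rule is applied is the date of actual dosing. Under SAP 3.7.1, Study Day 1 "is defined as the day when the first dose of study drug (ie, E/C/F/TAF) was taken", so it need not be the date of the Day 1 visit.

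On timing, Protocol 3.2 says that subjects "will switch from their current regimen consisting of FTC/TDF or ABC/3TC plus a third antiretroviral agent to E/C/F/TAF FDC on Day 1". Protocol 5.1 adds: "Initiation of treatment with the study drug must take place within 24 hours after the Day 1 visit". I found no sentence in either document that ties the last dose of the old regimen to the day before the first dose of study drug.

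The only provision for incomplete ARV dates is SAP Appendix 5 item 32: "Non-study drug ARVs collected in prior ARV form with start date and stop date completely missing are considered" not to be concomitant. It does not say whether such a record belongs to the pre-switch regimen, and it does not cover a partial end date.

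**The concern.** The primary objective and inclusion criterion 4 both describe the population by the regimen it switches from: FTC/TDF or ABC/3TC plus a third agent. A reader of the study report will want to see how many subjects came from each backbone and third agent. Only the SAP 7.5.1 table is planned to show this by class and agent. The baseline characteristics in SAP 5.2 carry just a flag for current indinavir, lopinavir or abacavir.

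A rule that demands an interval of exactly one day works only if every site records that interval. If it does not, the table under-counts agents with no sign that it has done so, because the affected subjects stay in the Safety Analysis Set and simply have no entry, or an incomplete one. The rule operates on each drug record separately, so a two-component regimen can lose one component and keep the other.

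**Working it through.** The plan states no figure on this point, so there is none to reproduce. The check applies the date rule to the dates that the protocol permits.

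**Inputs**
- Rule (SAP 7.5.1): counted if first dose date − ARV end date = 1 day.
- First dose date (Protocol 5.1, SAP 3.7.1): with V as the Day 1 visit date, a start within 24 hours falls on V or V+1.
- End date of the old regimen (Protocol 3.2): not fixed. I take it to lie between V−1 and the first dose date.

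**Result**

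| First dose | Old ARV ends | Gap (days) | Counted by 7.5.1 |
|---|---|---|---|
| V | V−1 | 1 | yes |
| V | V | 0 | no |
| V+1 | V−1 | 2 | no |
| V+1 | V | 1 | yes |
| V+1 | V+1 | 0 | no |

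Three of the five patterns fall outside the rule. This counts date patterns and says nothing about how many subjects follow each one.

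**Two further cases.** If FTC/TDF ends on the first dose date and the third agent ends the day before, the gaps are 0 and 1, and only the third agent is tabulated. If an end date has only month and year, an exact-day comparison cannot be made and the record is not counted.

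**How the SAP treats similar questions elsewhere.** Appendix 5 item 33 counts a lipid-modifying drug as in use at study entry if it started on or before the first dose date and was ongoing or ended on or after that date. A drug stopped on the dosing day is therefore an entry drug there, but not in 7.5.1. SAP 7.5.2 resolves partial dates by month and year, for non-ARV medications only. Item 33 could not simply be copied, because it would miss an ARV that ended the day before the first dose.

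**Scale.** The documents give no distribution of stop dates and no eCRF instructions for recording them. With the planned 64 subjects (SAP 1.3), and with the counts below assumed for illustration:
- 0 affected: 0%
- 1 affected: 1/64 = 1.6%
- 5 affected: 5/64 = 7.8%
- 10 affected: 10/64 = 15.6%

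**The case against.** The strongest reply is that little depends on this table. It is descriptive, no inference is attached to it, and every ARV record is listed whatever its dates, so no entry-regimen data are lost. Eligibility is confirmed before enrolment (Protocol 5.1), without this table. The Week 12 PVR definition in SAP 6.1.1.1 does not use the pre-switch variable, and no subgroup analyses are planned. All of that stands, and it sets the severity.

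It can also be said that the failing patterns may be rare. A gap of 0 means the old regimen and study drug were recorded on the same date, although Protocol 5.4 prohibits other HIV medication. A gap of 2 means a calendar day with no recorded ARV. Neither pattern is shown to be common, and sites may have entered the day before the first dose throughout. That stands too: the number affected could be zero.

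A reader might infer something stronger, namely that the rule would fail to pick up a Stribild or Descovy user and so alter the Full Analysis Set and the PVR denominator. The documents do not support this. SAP 3.1.2 excludes "Subjects who took Stribild or Descovy as part of the baseline antiretroviral (ARV) regimen and thus violated the inclusion criterion"; it neither cites 7.5.1 nor gives a stop-date rule. SAP 6.1.4.1 refers to these subjects as already excluded and returns them in a sensitivity analysis. The abacavir, indinavir and lopinavir flag in Appendix 5 item 41 likewise refers to baseline without using the one-day match. SAP 6.1.1.3 does mention stratifying by prior regimen, but for a log-rank test between two treatment groups that this single-arm study does not have, and without reference to 7.5.1.

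What the reply does not remove is that the rule is stated as an equality and gives a wrong table whenever a permitted date pattern differs from it.

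**Conclusion.** The point holds as a minor defect in one descriptive table. SAP 7.5.1 accepts only a one-day gap. The protocol also permits gaps of 0 and 2 days, and a partial end date cannot be matched. ARV records of those kinds would be left out of the only planned summary of entry regimens by class and agent, and some subjects could be shown with an incomplete regimen.

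The conclusion rests on reading the definition literally, as the only one the SAP gives, and on the protocol not fixing the old regimen's last day. The documents do not say how many subjects are affected, and zero is possible. Each one would be 1.6% of 64. The primary endpoint, the analysis sets and the ARV listing are not touched by this rule.

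**What to change.** In SAP 7.5.1, define pre-switch ARVs record by record as every nonstudy-drug ARV that started before the first dose date and whose end date falls from 2 days before the first dose date onward. This includes an end date on the first dose date and records marked ongoing. Include a partial end date when its month and year are compatible with that window. All five patterns in the table above would then be counted, and components with different end dates inside the window would stay together.

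For any treated subject with no qualifying record, query the dates and show the subject in a row labelled as not determined, so that the table accounts for everyone in the Safety Analysis Set.

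Taking only the records with the latest end date would not do. With components ending on different days it would keep one and drop the other, which is the fault to be removed.

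The cost is one SAP paragraph and a small change to the derivation, with no new data collection beyond the queries. The partial-date rule may admit an ARV that in fact stopped earlier in the same month, and the listing allows such records to be checked. The Stribild/Descovy exclusion in SAP 3.1.2 need not be changed for this purpose.

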### **7.5.2. Concomitant Non-Antiretroviral Medications**

Concomitant non-ARV medications (ie, medications other than study drug that are taken while receiving study drug) will be coded using the WHO Drug Dictionary. The WHO preferred name and drug code will be attached to the clinical database. Use of concomitant medications from Study Day 1 up to the date of last dose of study drug will be summarized (number and percentage of subjects) overall and by Parts 1 and 2 by preferred name. Multiple drug use (by preferred name) will be counted once only per subject. The summary will be sorted alphabetically by decreasing total frequency within a class.

If the start or stop date of non-ARV medications is incomplete, the month and year (or year alone if month is not recorded) of start or stop date will be used to determine whether the non-ARV medications are concomitant or not as follows. The medication is concomitant if the month and year of start or stop (or year of the start or stop) of the medication do not meeting any of following criteria:

- The month and year of start of the medication is after the date of the last dose of study drug
- The month and year of stop of the medication is before the date of the first dose of study drug

If the start and stop date of non-ARV medications are not missing, the start date is not after last dose date and the stop date is not before first dose date, or the non-ARV medications are marked as ongoing and start date is on or before last dose date, the non-ARV medications are concomitant.

Summaries of concomitant non-ARV medications will be provided for the Safety Analysis Set. Subjects with any concomitant non-ARV medications will be listed. No inferential statistics will be provided.

**7.6. Electrocardiogram Results**

The number and percentage of subjects in the Safety Analysis Set with an investigator's ECG assessment of normal, abnormal but not clinically significant, or abnormal and clinically significant will be summarized overall and by Parts 1 and 2 and by baseline ECG result for each visit. No inferential statistics will be provided.

A listing of safety ECG results will be provided including treatment, assessment date and time, and ECG results.

**7.7. Other Safety Measures**

A data listing will be provided for subjects experiencing pregnancy during the study.

**7.8. Subject Subgroup for Safety Endpoints**

Not applicable.

**7.9. Changes From Protocol-Specified Safety Analyses**

No change from protocol-specified safety analyses is planned.

## 8. PATIENT REPORT OUTCOMES

The Patient reported outcomes (PROs) include: (1) Visual Analogue Scale (VAS) adherence questionnaires; (2) Short Form-36 Version 2 Health Survey (SF-36); (3) HIVTSQs Status version (at Day 1 only)/HIVTSQc Change version (post-Day 1); (4) FACIT-F; (5) EQ-5D. Unless otherwise stated, multiple responses and out of range responses will be set to missing and missing responses will not be imputed. The Safety Analysis Set will be used in all analyses. No inferential statistics will be provided. All reported data will be listed.

### 8.1. Adherence – Visual Analogue Scale (VAS) Adherence Questionnaire

The VAS adherence questionnaire is a 3-item, self-reported questionnaire that assesses the degree to which ARV medication was taken in the past 30 days.

For the VAS, the subject is asked to describe their adherence to their ARV regimen by using a linear scale (0% – 100%) to indicate what percent of medications was taken in the last 30 days (0% – taken none of prescribed anti-HIV medication, and 100% – taken all doses of prescribed anti-HIV medication). Two additional questions ask how many days the subject has missed medications in the last 30 days and how many days the subject has missed medications in the last 4 days.

#### 8.1.1. VAS Statistical Method

The VAS (%) absolute value and its change from baseline at each visit will be summarized overall and by Parts 1 and 2 using descriptive statistics. Number of days with missed doses in the past 30 days and past 4 days will be summarized categorically (eg, < 2, 2 to < 4, 4 to < 6, ≥ 6 for the past 30 days; 0 and > 0 for the past 4 days) at each visit.

### 8.2. SF-36 (Version 2) Health Survey

The SF-36 Version 2 is a 36-item, self-reported, generic, comprehensive, and widely used questionnaire that is designed to measure health-related quality of life in the general population, as well as in subject groups with diverse chronic diseases including HIV/AIDS. Responses from the 36 items are used to construct 8 health domains including physical functioning, social functioning, general health, vitality, bodily pain, mental health, role capacity-physical, and role capacity-emotional. Furthermore, 2 summary scores, the Physical Component Summary (PCS) score and Mental Component Summary (MCS) score, aggregate information from the 8 SF-36 domains in a way that captures 80% to 85% of the variance in the 8 domains.

#### 8.2.1. Scoring the SF-36

The 8 domains and 2 component summary scores of the SF-36 will be calculated according to “How to Score Version 2 of the SF-36 Health Survey (Chapters 6 and 7)” {[Maruish 2011](#)} published by QualityMetric Inc *{using 2009 population norms}*. Scores for each of the 8 domain including PCS and MCS range from 0 to 100 with higher score indicating a better functioning.

#### 8.2.2. SF-36 Statistical Analysis Method

Scores for each domain, PCS, and MCS will be summarized overall and by Parts 1 and 2 for each visit using descriptive statistics (n, mean, SD, median, Q1, Q3, minimum and maximum).

A by-subject listing for the scores for each domain, PCS, and MCS will be provided by subject ID number and visits in chronological order.

### 8.3. HIV Treatment Satisfaction Questionnaire

At baseline, a treatment satisfaction scale total will be calculated as the sum of the responses to the 10 question items on the HIVTSQs form (range from 0 to 60). At postbaseline visits, a treatment satisfaction scale total in change will be calculated as the sum of the responses to the 10 question items on the HIVTSQc form (range from -30 to 30).

Additionally, two subscale scores, one for general satisfaction/clinical and another for lifestyle/ease will be computed. Each subscale ranges from 0 to 30 on the HIVTSQs form and from -15 to 15 on the HIVTSQc form.

Table 8-1 lists the questions, possible responses for both the status and change questionnaires, as well as the subscale each question belongs to.

